2.1.1 General definitions

For more information, see the GSK SAP.

2.2 Analysis sets

2.2.1 All Treated Population

The All Treated population is defined as all patients who receive at least one dose of study treatment. An incorrect treatment schedule or drug administration or an early termination of treatment will not result in exclusion of patients from this population.

2.2.2 Safety Population

The Safety population consists of all patients who received at least one dose of study treatment. All safety data will be analysed using the Safety population.

In this study, the All Treated population and Safety population are identical.

2.2.3 Dose Limiting Toxicity Evaluable Population

The Dose Limiting Toxicity (DLT) Evaluable population is defined as those Part 1 patients fulfilling the All Treated population criteria, and having received an adequate treatment for the first 28 days to enable an appropriate evaluation of study drug related DLTs. Adequate exposure during the first 28 days will be defined as having received > 75% of planned study drug doses, exclusive of missed doses due to treatment-related toxicity. Patients who are either withdrawn or dose reduced due to toxicity during the first 28 days will be included in the DLT evaluable population. Any patient from Part 1 in the ‘All Treated’ population who experiences a DLT, as defined in section 3.3 of the protocol, will also be included in the DLT evaluable population regardless of exposure.

2.2.4 Pharmacokinetic Population

The Pharmacokinetic (PK) population is defined as those patients fulfilling the All Treated population criteria and for whom pharmacokinetic sample(s) are obtained and analysed. This population will be used for the primary, secondary PK endpoints, [REDACTED] analyses.

Patients may be removed from the estimation of certain PK parameters on an individual basis depending on the number of available blood samples. Specific time points might be removed from the analysis set if technical issues with the sample are reported (e.g. sampling issues, missing information) or if LLOQ sample is observed in between measurable concentrations. These patients and concentration data points will be identified at the time of analysis.

2.2.5 Response-evaluable Population

The Response-evaluable population is defined as those patients fulfilling the All Treated population criteria with a pre-dose and at least 1 post-dose disease efficacy assessment. In addition, for patients evaluated by RANO criteria, their disease must be ‘measurable’ at baseline to be included in the Response-evaluable population. This population will be used for sensitivity analysis on the efficacy endpoints.

2.2.6 Subgroup of interest

There are no formal plans for examining subgroups.

2.3 Patient disposition, demographics and other baseline characteristics

Age (years, months or days) will be collected in CRF based on the derivation in the table below. There will be 2 age variables calculated in ADS, age in years, and derived age: age in years, months and days.

AGE in years = round ((AGEY*365.25+AGEM*30.4375+AGED)/365.25, 0.1)

where AGEY for age in years; AGEM for age in months; AGED for age in days.

If Age in years > 0, then AAGE = floor(Age in years);
Else if Age in months > 0, then AAGE = floor(Age in months);
Else if Age in days > 0, then AAGE = floor(Age in days).

Listing will include the birth year and age as collected.

For details, refer to section 10.3 of GSK SAP.

In addition to the analysis mentioned in section 10.3 of GSK SAP , the similar summary of subject demographics, baseline characteristics, disease history, prior anti-cancer treatments and change from baseline in Karnofsky and Lansky performance status will be carried out by pooled disease cohort (as defined in [section 2.1](#)).

2.3.1 Patient disposition

For details, refer to study GSK SAP.

Additionally, the similar analysis will be carried out for subject disposition by pooled disease cohort (as defined in [section 2.1](#)).

2.3.2 Protocol deviation

The number and percentage of patients in the All Treated population with any major protocol deviation will be tabulated by deviation category (as specified in the study protocol deviation plan).

Similarly, a separate table and listing will be provided for protocol deviations related to COVID-19.

2.4 Treatments (study treatment, rescue medication, concomitant therapies, compliance)

Refer to GSK SAP for more information.

For pooled disease cohort, similar summary of treatment exposure will be carried out for overall duration of exposure and also for dose reductions/interruptions.

Dose intensity and relative dose intensity will be summarized by age categories (<12 years and ≥12 years)

2.5 Analysis of the primary objective

2.5.1 Primary endpoint

Refer to study GSK SAP.

2.5.2 Statistical hypothesis, model, and method of analysis

There are no formal tests of hypotheses planned for this trial. With respect to the primary objectives and endpoints, the primary focus will be on determining the maximum tolerated dose (or recommended dose based on available safety, PK, and response data), the safety profile, and PK/PD relationship of dabrafenib in pediatric patients with advanced BRAF V600-mutation positive solid tumors. Most analyses will be descriptive or exploratory.

2.5.3 Handling of missing values/censoring/discontinuations

Refer to study GSK SAP.

Supportive analyses Refer to study GSK SAP.

2.6 Analysis of the key secondary objective

2.6.1 Secondary endpoint

The All Treated population will be used for all efficacy analyses.

Overall response rates along with 95% confidence intervals will be separately calculated for all the disease cohorts including the LGG, HGG, LCH and Other disease cohorts.

Efficacy assessments are based on RANO criteria for LGG and HGG patients. In addition, for LGG patients, the updated RANO criteria will be used for independent review. For LCH patients, the response assessment criteria are described in Appendix 2 of the protocol. For patients with other solid tumor, efficacy assessments are based on RECIST 1.1.

Refer to study GSK SAP for additional details.

2.6.2 Handling of missing values/censoring/discontinuations

Refer to study GSK SAP.

2.8 Safety analyses

The Safety population will be used for all safety analyses.

Refer to study GSK SAP for additional details.

2.8.1 Adverse events (AEs)

AEs will be graded according to the CTCAE, Version 4.0. Adverse events will be coded to the preferred term (PT) level using the MedDRA dictionary. The latest available MedDRA version at the time of the analyses will be used. The MedDRA version used for reporting will be specified as a footnote in the applicable tables/listings.

For more details, refer to study GSK SAP.

Similar summary of overview of AEs for pooled disease cohorts will be generated. Moreover, summary of AEs regardless of relationship by preferred term and maximum grade and summary of AEs suspected to be related to study drug by preferred term will also be carried out by pooled disease cohort.

In addition, For the legal requirements of ClinicalTrials.gov and EudraCT, two required tables on on-treatment adverse events which are not serious adverse events with an incidence greater than 5% and on on-treatment serious adverse events and SAE suspected to be related to study treatment will be provided by system organ class and preferred term on the safety set population.

If for a same patient, several consecutive AEs (irrespective of study treatment causality, seriousness and severity) occurred with the same SOC and PT:

- a single occurrence will be counted if there is ≤ 1 day gap between the end date of the preceding AE and the start date of the consecutive AE
- more than one occurrence will be counted if there is > 1 day gap between the end date of the preceding AE and the start date of the consecutive AE

For occurrence, the presence of at least one SAE / SAE suspected to be related to study treatment / non SAE has to be checked in a block e.g., among AE's in a ≤ 1 day gap block, if at least one SAE is occurring, then one occurrence is calculated for that SAE.

The number of deaths resulting from SAEs suspected to be related to study treatment and SAEs irrespective of study treatment relationship will be provided by SOC and PT.

2.8.2 Seriouese Adverse events

For SAEs, in a similar way as of AEs, summary by preferred term regardless of relationship to study drug and also summary for suspected study drug related SAEs by preferred term will be carried out by pooled disease cohorts.

Refer to study GSK SAP for additional details.

2.8.3 Deaths

Refer to study GSK SAP for additional details.

2.8.4 Laboratory data

Refer to study GSK SAP for additional details.

Summary of shift from baseline, based on CTC grade will be carried out for Hematology and Biochemistry laboratory parameters by pooled disease cohorts instead of treatment.

2.8.5 Other safety data

Refer to study GSK SAP for additional details.

2.8.5.1 ECG and cardiac imaging data

[figure not shown]
The corrected QT duration for heart rate (QTcB) will be manually calculated using Bazett's formula if the data is not available. See Appendix 5.1.

[figure not shown]

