Cardiovascular effects: Data from preclinical studies with dabrafenib suggest the potential for cardiovascular effects, including cardiac valve effects in the 28 day dog study, coronary vascular effects in the 7 day dog study, hepatic vascular effects in a 10 day rat study, increased incidence of minimal cardiomyopathy in male rats and mild increases in heart rate in single dose studies in dogs and rats. In a 13-week oral toxicity study in dogs right atrial wall thickening characterized microscopically by fibrovascular proliferation (transmural granulation tissue) was observed. In the ongoing monotherapy clinical studies, 3 (<1%) non-serious valvular abnormalities meeting stopping criteria have been identified to date; two of these subjects had baseline valvular abnormalities. Additionally, a blinded independent review of available echocardiogram results from subjects participating in the phase 2 BREAK-2 study was performed to further examine the effect of dabrafenib on valvular function. No persistent findings suggestive of a drug effect were observed. Because valvular abnormalities were observed in a minority of subjects in the integrated dabrafenib population, and the results of the central analysis in BREAK-2 were not suggestive of a drug effect, valvular toxicity is no longer considered an AE of special interest for dabrafenib. Subjects with clinically significant baseline cardiac abnormalities are excluded from the study. Safety evaluations include physical examination, 12-lead electrocardiogram (ECG) and echocardiogram (ECHO) monitoring as well as AE reporting.

Respiratory Effects: Lobar bronchoalveolar inflammation has been observed in dogs, with shallow and/or labored breathing noted during the treatment phase in 2 dogs given dabrafenib for 13 weeks. Respiratory changes are being monitored through medical history and physical examination. There have been no corresponding clinical findings identified in clinical trials to date.

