5.3.3.1.4 Other Safety Measures

Performance status (Karnofsky/Lansky) assessments will be summarized by the originally assigned dose level. Vital signs, ECG, and ECHOs will be summarized at all measured time points. A descriptive summary including change from baseline pre-dose will also be presented. Further details will be provided in the SAP.

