- During treatment subjects should be monitored as clinically appropriate. Complete blood cell counts should be performed as clinically indicated. Following discontinuation of dabrafenib monitoring for non-cutaneous secondary/recurrent malignancies should continue for up to 6 months or until initiation of another anti-neoplastic therapy, whichever comes first. Any non-cutaneous secondary/recurrent malignancy should be reported as a protocol-specific SAE and treated according to standard clinical practice.
- See [Appendix 6](#) for French country specific guidelines.

Vital Signs

- Vital sign measurements will include systolic and diastolic blood pressure, temperature and pulse rate.
- If a subject develops a fever, refer to Section 3.7.1 for management guidelines.

Electrocardiogram (ECG)

- A single 12-lead ECG will be obtained at each time point during the study using an ECG machine that automatically calculates the heart rate and measures PR, QRS, QT, and

QTcB intervals. Refer to [Section 3.7.4.4](#) for QTcB withdrawal criteria and additional QTcB readings that may be necessary.

Echocardiography (ECHO)

- ECHOs will be performed to assess cardiac ejection fraction. The echocardiographer's evaluation should include an evaluation of left ventricular ejection fraction. Post-dose ECHOs should be compared to baseline to note if there are any changes.
- Copies of all ECHOs and cardiology consultations performed on subjects who experience a >10% absolute decrease in LVEF from baseline and whose cardiac ejection fraction is less than institution's LLN will be required by Novartis for review.

Clinical Laboratory Assessments

Hematology, clinical chemistry and additional parameters to be tested are listed below:

Hematology			
Platelet Count:	Red blood cell (RBC) Indices (at screening and if hemoglobin decrease ≥ 2 g/dL compared to baseline):		Automated White Blood Cell (WBC) Differential:
RBC Count	MCV		Neutrophils
WBC Count (absolute)	MCH		Lymphocytes
Hemoglobin	MCHC		Monocytes
	Reticulocyte Count		Eosinophils
			Basophils
Clinical Chemistry			
BUN	Potassium	AST	Total and direct bilirubin ^a
Creatinine	Chloride	ALT	Uric Acid
Glucose	Total CO ₂	Alkaline phosphatase	Albumin
Sodium	Calcium		Total Protein
Magnesium	Phosphate		
Other tests			
Pregnancy tests			
Amylase and lipase [monitor via local laboratory where appropriate to evaluate certain AEs (i.e., abdominal pain, pancreatitis, etc.)]			

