5.1 Laboratory parameters derivations

[figure not shown]
Bazett's formula is as follows:

$$QT_{cB} = \frac{QT}{\sqrt{RR}}$$

where QT_{cB} is the QT interval corrected for heart rate, QT is the measured QT interval and RR is the interval from the onset of one QRS complex to the onset of the next QRS complex (all measurements in seconds). RR is often derived from the heart rate (HR) as 60/HR. QT interval is collected in milliseconds on the CRF and will be displayed in milliseconds in the outputs.

6 Reference

Refer to the study GSK SAP.

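### QTc is Bazett-only in the supplied protocol and SAP; a cube-root sensitivity summary beside heart-rate change would show how far QTcB change from baseline depends on heart rate

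*SAP*

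**What the plan says.** Protocol 6.3 describes the source of the data: "A single 12-lead ECG will be obtained at each time point during the study using an ECG machine that automatically calculates the heart rate", along with PR, QRS, QT and QTcB. No other QT correction is listed.

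SAP 2.8.5.1 states: "The corrected QT duration for heart rate (QTcB) will be manually calculated using" Bazett's formula when the recorded value is missing. This is a fallback for a missing value, but the recorded and the calculated value use the same correction. SAP 5.1 gives it as QT divided by the square root of RR, notes that "RR is often derived from the heart rate (HR) as 60/HR", and adds that "QT interval is collected in milliseconds on the CRF and will be displayed in milliseconds in the outputs".

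The entry criterion (Protocol 4.2.1) and the withholding table (Protocol 3.7.4.4, Table 3-6) are also written in QTcB.

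On reporting, Protocol 5.3.3.1.4 says: "Vital signs, ECG, and ECHOs will be summarized at all measured time points", and "A descriptive summary including change from baseline pre-dose will also be presented". Protocol Section 2 lists ECG under both the primary and the longer-term safety endpoints.

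**The concern.** The Bazett correction depends more steeply on heart rate than the cube-root correction does. If heart rate at follow-up ECGs differs systematically from baseline, part of the change in QTcB may come from rate. The trial has one arm, so no concurrent control shares the shift and removes it.

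The protocol gives some reason to expect heart rate to move. Section 1.3 reports pyrexia in 27% of adults, with median first onset at 3 weeks, and ECGs are scheduled at Days 8, 15 and 22 (Table 3-7). The same section cites "mild increases in heart rate in single dose studies in dogs and rats". Entry is from 12 months of age and ECGs continue every 12 weeks after Week 48 (Table 3-9), so some children will grow during follow-up. That heart rate falls as they grow is an assumption; the documents do not say so.

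The two influences act in opposite directions. A rise in rate could look like prolongation, and a fall could hide one. With a single correction the reader cannot tell how much of a QTcB change to attribute to rate.

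**Working it through.** The plan states no QTc result, expected heart-rate shift or QT-RR exponent, so there is no figure of its own to reproduce.

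**Inputs from the documents.** QTcB = QT/RR^(1/2) and RR = 60/HR (SAP 5.1). QT is on the CRF (SAP 5.1) and heart rate comes from the ECG machine (Protocol 6.3).

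**Comparator.** QTcF = QT/RR^(1/3).

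**Step 1: ratio of the two corrections.** For any QT, QTcB/QTcF = RR^(-1/6) = (HR/60)^(1/6). This is an identity. It gives 1.070 at 90 bpm, 1.122 at 120 bpm and 1.165 at 150 bpm.

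**Step 2: change from baseline with no drug effect.** Set QT = 400 ms × RR^b. Then QTcB = 400 × (HR/60)^(1/2 − b) and QTcF = 400 × (HR/60)^(1/3 − b). The 400 ms, the heart rates and b (0.30 to 0.50) are assumptions.

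Example, HR 90 to 120 with b = 1/3: QTcB goes from 400 × 1.0699 = 428.0 ms to 400 × 1.1225 = 449.0 ms, a change of +21.0 ms. QTcF stays at 400 ms.

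| HR (bpm) | b | Change in QTcB (ms) | Change in QTcF (ms) | Difference (ms) |
|---|---|---|---|---|
| 90 to 105 | 0.30 | +13.6 | +2.1 | 11.5 |
| 90 to 105 | 1/3 | +11.1 | 0.0 | 11.1 |
| 90 to 105 | 0.40 | +6.5 | −4.0 | 10.5 |
| 90 to 105 | 0.50 | 0.0 | −9.5 | 9.5 |
| 90 to 120 | 0.30 | +25.7 | +3.9 | 21.8 |
| 90 to 120 | 1/3 | +21.0 | 0.0 | 21.0 |
| 90 to 120 | 0.40 | +12.2 | −7.4 | 19.6 |
| 90 to 120 | 0.50 | 0.0 | −17.5 | 17.5 |
| 110 to 85 | 0.30 | −22.7 | −3.5 | −19.2 |
| 110 to 85 | 1/3 | −18.6 | 0.0 | −18.6 |
| 110 to 85 | 0.40 | −10.8 | +6.7 | −17.5 |
| 110 to 85 | 0.50 | 0.0 | +15.9 | −15.9 |

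Three further shifts fall within the same range. In absolute size the difference is 14.2 to 19.0 ms for HR 110 to 140, 11.0 to 14.0 ms for 120 to 100, and 13.9 to 16.3 ms for 100 to 80.

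**Step 3: reading.** The gap between the two corrections varies little with b and is 9.5 to 21.8 ms over shifts of 15 to 30 bpm. The error in QTcB itself varies a great deal with b: from 0 to 25.7 ms for HR 90 to 120. For b strictly between 1/3 and 1/2 the two corrections err in opposite directions, so together they bracket the rate-free change. Outside that range they need not, as the b = 0.30 rows show.

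**The case against.** The strongest reply is that the supplied SAP cannot show what is missing. Its Introduction says that it covers only changes and additions, that all outputs in the previous SAP are still required, and that the GSK SAP holds the detail; SAP 2.8.5 refers there again for other safety data. The public copy also has gaps around the ECG sentence. A reader might infer that the trial's analysis plan has no second correction. The documents do not support that, so the point is conditional on a check of the GSK SAP.

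A reader might also infer that QTcB is biased here. That is not shown. If QT follows RR^0.5 there is no carry-over, and the cube-root correction would be the one in error. This part stands, and it is why both corrections should be shown and neither should replace the other.

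The case for a heart-rate shift is indirect. The fever rate is from adults, 74% of first episodes lasted 5 days or less, and nothing shows how many children would be febrile at a scheduled ECG. The animal finding is mild and comes from single-dose studies. A reader might further infer that QTc outlier counts would be distorted, but no QTc outlier table appears in the supplied text.

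Finally, pulse rate is a vital sign (Protocol 6.3) and is itself summarised with change from baseline, so a shift in rate would be visible. That is true, but a separate mean change in rate does not say how much of the QTcB change belongs to it.

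**Conclusion.** The point holds as a cheap improvement. In the supplied documents QTc is Bazett throughout, change from baseline is planned, there is no control arm, and the data for a second correction are already collected. The choice of correction can move a mean change from baseline by about 10 to 22 ms, given heart-rate shifts of 15 to 30 bpm and a reference QTc of 400 ms, all assumed. The bias in QTcB alone depends on the unknown QT-RR relation and may be zero.

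The consequence is limited. SAP 2.5.2 plans no hypothesis test, and the ECG summaries are descriptive. Using QTcB in the analysis is consistent with the entry and withholding criteria, and nothing here shows that those criteria or the recorded QTcB values are wrong.

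**What to change.** First check the GSK SAP. If it already has a second QT correction, the point is closed.

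If not, add QTcF = QT/RR^(1/3), with RR = 60/HR where RR is not recorded, to SAP 2.8.5.1 and 5.1 as a sensitivity analysis. Present value and change from baseline for QTcB and QTcF at each scheduled ECG, beside the change in heart rate from the same ECG. Add outlier categories for QTcF only if the GSK SAP tabulates them for QTcB. State in advance that similar results indicate little dependence on rate, and that divergence is to be read against the heart-rate change and not as a drug effect. Leave the QTcB entry and withholding criteria unchanged.

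The cost is one derived variable and a repeat of the descriptive tables, with no new measurement. The downside is a second set of QTc results to reconcile in the clinical study report.

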2.8.5.2 Vital signs

[figure not shown]
Refer to study GSK SAP.

[figure not shown]
2.9 Pharmacokinetic endpoints

[figure not shown]
Refer to study GSK SAP.

2.12 Interim analysis

A number of previous interim analyses have been performed for Health Authority interactions, or when a specified minimum follow up was reached in certain cohorts. These interim analyses are documented in separate CSRs.

No efficacy or futility conclusions were made based on these interim analyses.

3 Sample size calculation

Refer to study GSK SAP; Section 5.

4 Change to protocol specified analyses

No change from protocol specified analysis except [REDACTED]
[REDACTED] reporting of protocol deviations related to COVID-19.

[figure not shown]
5 Appendix

[figure not shown]
5.1 Laboratory parameters derivations

[figure not shown]
Bazett's formula is as follows:

$$QT_{cB} = \frac{QT}{\sqrt{RR}}$$

where QT_{cB} is the QT interval corrected for heart rate, QT is the measured QT interval and RR is the interval from the onset of one QRS complex to the onset of the next QRS complex (all measurements in seconds). RR is often derived from the heart rate (HR) as 60/HR. QT interval is collected in milliseconds on the CRF and will be displayed in milliseconds in the outputs.

6 Reference

Refer to the study GSK SAP.
